17.6.3 Extracted nicotine versus nicotine exposure

Correlation between total extracted amount of nicotine and C_{max} and AUC_{inf} will be analyzed using correlation analysis as further described in the SAP.

17.6.4 Urge to snus

Subjective urge to snus measured through VAS will be summarized for each IP using summary statistics both as a total score and the min and max score during the IP administration phase. Further analyses will be described in the SAP.

17.7 Analysis of exploratory endpoints

17.7.1 Pharmacodynamic effect of nicotine

Analyses of pulse rate as measure of pharmacodynamic effect of nicotine will be further described in the SAP.

17.7.2 Comparison of PK plasma samples versus DBS samples

The correlation for C_{max} and AUC_{inf} between DBS samples and plasma samples for ZYN Moist 7 mg, ZYN Dry Mini 6 mg and Longhorn 18 mg will be analyzed with correlation analysis.

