Blood samples for assessment of plasma levels of nicotine will be collected at pre-defined time points from pre-dose to 6 hours after IP administration. In addition, urge to snus (using VAS) and pharmacodynamic effect of nicotine (by measuring pulse rate) will be determined.

Investigational Product (IP), dosage and mode of administration

1: ZYN Moist Smooth containing 7 mg nicotine per portion

- 2: ZYN Moist Smooth containing 9 mg nicotine per portion
- 3: ZYN Moist Smooth containing 11 mg nicotine per portion
- 4: ZYN Dry Mini Smooth containing 3 mg nicotine per portion
- 5: ZYN Dry Mini Smooth containing 6 mg nicotine per portion

Reference product

6: Longhorn Pouch Natural containing 18 mg nicotine per portion

Duration of treatment

The participating subjects will receive study product at 6 occasions, in a cross-over fashion, with 60 minutes of treatment per occasion.

Duration of each subject's involvement in the study

Each subject will participate in the study for a period of approximately 6 weeks.

Pharmacokinetic (PK) assessments

Blood samples for analysis of PK parameters will be collected pre-dose, 5 min, 10 min, 15 min, 30 min, 45 min, 1h, 1h:15 min, 1h:30 min, 2h, 4h, 6h post-dose. The PK parameters in the study will include AUC_{inf} , AUC_{0-t} , C_{max} , T_{max} , and terminal half-life.

PK parameters (AUC_{inf} and C_{max}) calculated from plasma samples and dried blood spots (DBS) will be compared (reported separately).

Pharmacodynamic (PD) assessments

Continuous pulse rate

Pharmacodynamic effect of nicotine will be assessed by pulse rate measure.

Urge to snus

Urge to snus will be rated using VAS.

Nicotine extraction assessment

Extracted amount of nicotine (mg/unit) and extracted fraction (%) will be assessed

Statistical methods

No formal sample size calculation has been performed for this study. However, the proposed sample size is considered sufficient to provide adequate information for the study objectives.

Continuous data will be presented in terms of evaluable and missing observations, arithmetic mean, SD, median, minimum and maximum value, Q1-Q3 (interquartile range [IQR]). In addition, for the parameters AUC and C_{max} the geometric mean and coefficient of variation (CV) will be presented.

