7.3 Exploratory objectives

The exploratory objectives are:

- 1. To compare pharmacodynamic effects of nicotine by measuring pulse rate.
- 2. To compare the C_{max} and AUC_{inf} between plasma samples and Dried Blood Spot (DBS) samples for ZYN Moist 7 mg, ZYN Dry Mini 6 mg and Longhorn 18 mg.
- 3. To evaluate the early nicotine exposure for each product.

7.3.1 *Exploratory endpoints*

The exploratory endpoints are:

- 1. The difference in pulse rate measured using a pulse oximeter up to 2 hours after the start of the IP administration will be compared among the products.
- 2. The correlation for C_{max} and AUC_{inf} between DBS samples and plasma samples for ZYN Moist 7 mg, ZYN Dry Mini 6 mg and Longhorn 18 mg.

3. Pharmacokinetics of nicotine in plasma: AUC_{0-30min} for each product.

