11.5.2 Pharmacokinetic sampling using Dried Blood Spot technique

Blood samples for determination of concentrations of nicotine after administration of ZYN Moist 7 mg, ZYN Dry Mini 6 mg and Longhorn 18 mg will be collected using DBS for 18 consecutive subjects at pre-specified time-points; pre-dose (within 15 min prior to dose), and 5 min, 10 min, 15 min, 30 min, 45 min, 1h, 1h:15 min, 1h:30 min, 2h, 4h, 6h post-dose, see Table 8.1-2.

Following finger prick procedure with a lancet, the entire circle on the collection card should be uniformly saturated for each sampling timepoint. The card should be fully air-dried-horizontally at room temperature and stored away from direct sunlight.

For further details see lab manual.

DBS for determination of concentrations of nicotine will be analyzed by Department of Chemistry, Uppsala University.

The collection of whole blood samples on paper is known as DBS. DBS offers a number of advantages over conventional blood collection. As a less invasive sampling method, DBS offers simpler sample collection and storage and easier transport, with reduced infection risk of various pathogens, and requires only a few drops of blood. The DBS blood collection platform is rapidly becoming an important basis for quantitative analysis of biomarkers.

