15.7 Reporting and publication

15.7.1 Clinical study report

A clinical study report (CSR), in compliance with ICH-E3, describing the conduct of the study, any statistical analyses performed, and the results obtained, will be prepared by CTC. The report will be reviewed and approved by, as a minimum, the Principal Investigator, the Statistician and the Sponsor.

Results for the exploratory comparison of sampling technique between plasma sampling and DBS for nicotine concentrations will be reported separately.

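### The DBS–plasma objective is a comparison, but the endpoint and the analysis are a correlation, which cannot quantify a systematic difference between the two methods

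*Protocol*

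**What the plan says.** - **Objective.** Exploratory objective 2 (protocol 7.3, repeated in the synopsis) concerns two parameters, AUCinf and Cmax, and sets out to compare them "between plasma samples and Dried Blood Spot (DBS) samples for ZYN Moist 7 mg, ZYN Dry Mini 6 mg and Longhorn 18 mg".
- **Endpoint.** Exploratory endpoint 2 (7.3.1, repeated in the synopsis) is the correlation of these two parameters "between DBS samples and plasma samples for ZYN Moist 7 mg, ZYN Dry Mini 6 mg and Longhorn 18 mg".
- **Analysis.** Section 17.7.2 is headed as a comparison of the two kinds of sample. Its one sentence ends "Longhorn 18 mg will be analyzed with correlation analysis". It names no other statistic.
- **Data.** Under 11.5.2 the spot samples "will be collected using DBS for 18 consecutive subjects at pre-specified time-points", which match the plasma time points. They are taken "Following finger prick procedure with a lancet", so they are capillary whole blood. Plasma comes from a venous catheter (11.3.1).
- **Reporting.** Section 15.7.1 states: "Results for the exploratory comparison of sampling technique between plasma sampling and DBS for nicotine concentrations will be reported separately". Neither this section nor the synopsis, which also speaks of comparing the parameters, gives a method.
- **General summaries.** Section 17.1 provides geometric means and CVs for AUC and Cmax, arranged by treatment and assessment time, and individual listings. It does not mention sampling method or paired differences.

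**The concern.** Comparing two measurement methods raises two questions: how far apart are they on average, and how much does that difference vary from one pair to the next? A correlation answers neither. It reports how closely the points follow a straight line, whatever the slope and intercept of that line.

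Here the two samples differ in both matrix and site, so a systematic difference is plausible and is the natural first thing to look for. A high coefficient would be compatible with no difference, with DBS well below plasma, or with DBS well above it. The substudy would collect the pairs needed to tell these apart, while its only named between-method analysis could not.

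**Working it through.** The protocol gives no figure for this comparison, so there is none to reproduce. The check is of what the named statistic can show.

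**1. Invariance (no assumption about the data).** For any b > 0, corr(X, a + bY) = corr(X, Y). If DBS = 0.7 × plasma exactly, then r = 1.00. A constant scale factor leaves r unchanged on raw or log values. A constant shift leaves the Pearson r on raw values and the Spearman coefficient unchanged.

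**2. One simulated sample of 18 pairs.** The same data were rescaled or shifted, and Lin's concordance was computed as a contrast because it does respond to bias:

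| Change applied to DBS | Pearson r | Spearman | Concordance |
|---|---|---|---|
| none | 0.9514 | 0.9071 | 0.95 |
| × 0.7 | 0.9514 | 0.9071 | 0.69 |
| × 0.5 | 0.9514 | 0.9071 | 0.36 |
| + 2 | 0.9514 | 0.9071 | 0.86 |

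**3. Repeated sampling.** Assumptions, none from the protocol: between-subject CV 40%, error CV 10% in each method, 18 pairs, 5,000 repeats. Medians:

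| True DBS/plasma ratio | r | Concordance | Geometric mean ratio |
|---|---|---|---|
| 1.0 | 0.94 | 0.93 | 1.00 |
| 0.8 | 0.94 | 0.78 | 0.80 |
| 0.7 | 0.94 | 0.62 | 0.70 |
| 0.5 | 0.94 | 0.31 | 0.50 |
| 1.3 | 0.94 | 0.73 | 1.30 |

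Median r moved only with the assumed spread between subjects: 0.90, 0.94 and 0.96 at CVs of 30%, 40% and 50%.

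**4. Precision of r.** For an assumed observed r of 0.90 with n = 18, Fisher z = 1.472 and its half-width is 1.96/√15 = 0.506. The limits 0.966 and 1.978 transform back to r = 0.75 to 0.96.

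**5. Precision of the ratio with the same 18 pairs.** The 95% CI is the ratio multiplied and divided by exp(t × s/√18), with t = 2.11 on 17 degrees of freedom and s = √ln(1 + CV²).

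- Assumed paired CV 10%: s = 0.100, exp(2.11 × 0.100/4.243) = 1.05.
- Assumed paired CV 30%: s = 0.294, exp(2.11 × 0.294/4.243) = 1.16.

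The planned number of subjects is therefore enough to estimate a systematic difference within each product.

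**The case against.** **The general summaries may already show a shift.** If section 17.1 covers the DBS parameters, geometric means for both methods would be reported. On complete pairs the quotient of the two geometric means equals the paired geometric mean ratio, because exp(mean ln DBS) / exp(mean ln plasma) = exp(mean(ln DBS − ln plasma)). This stands. A reader might infer that the substudy leaves its objective wholly unanswered, and that goes too far. What is not planned is the ratio as a stated result, its interval, and the spread of the individual ratios.

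**Detail belongs to the SAP.** The opening of section 17 leaves technical elaboration to the SAP, and the SAP or the separate DBS report may add agreement measures. This is fair as to the type of correlation and any supporting statistics. It does not cure the mismatch, because the endpoint itself is defined in the protocol as a correlation. A SAP that only elaborated the correlation would follow the protocol and still not quantify the difference.

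**A constant ratio need not be an error.** Whole blood and plasma are different matrices, and the protocol does not claim that they read the same. A stable ratio could serve as a conversion factor. This stands, and is why the point is worded as a systematic difference rather than as bias in DBS. A conversion factor would still have to be estimated, with its spread.

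**Stronger readings that the protocol does not support.**

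- A reader might infer that the three products will be pooled, which would widen the range and could raise r. Section 17.7.2 does not say so. Pooling would give up to 18 × 3 = 54 pairs, three per subject and not independent, but this matters only if it is done.
- A reader might infer that a high r will be used to replace venous sampling. Section 11.5.2 lists general advantages of DBS, but no objective, endpoint or decision rule proposes replacement.
- A reader might infer that baseline correction differs between the matrices. Section 17.6.1 corrects AUCinf and Cmax for baseline, and nothing shows a different treatment for DBS.

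**Conclusion.** The point holds in this limited form. The objective calls for a comparison; exploratory endpoint 2 and section 17.7.2 fix a correlation as the only between-method analysis. The invariance result rests on no assumption: a constant ratio between DBS and plasma, whatever its size, leaves the coefficient untouched. The ratio of 0.7, the CVs and the r of 0.90 are illustrations and are not taken from the protocol.

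The reach is small. This is one exploratory objective in an 18-subject subset, reported separately, and no primary or secondary conclusion depends on it. Because the data are paired, the ratio could also be calculated later. It is still worth correcting beforehand, so that the planned result answers the stated objective.

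**What to change.** In exploratory endpoint 2 (7.3.1 and the synopsis) and in section 17.7.2, replace correlation as the analysis by:

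- the paired DBS/plasma geometric mean ratio of Cmax and of AUCinf, with 95% CI, for each product;
- Bland-Altman 95% limits of agreement on the log scale, back-transformed to ratios, for each product;
- if products are also pooled, a model on the log ratios with subject as a random effect;
- correlation kept as a descriptive statistic.

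The cost is analysis wording in the endpoint and in one section. It needs no further subjects, samples or assays, because the pairs are already part of the plan.

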17.7.3 Early nicotine exposure

 $AUC_{0-30min}$ will be analyzed as described in Section 17.6.1.

17.8 Analysis of Adverse events

An overview of all AEs, including SAEs, intensity, and deaths will be presented by SOC and PT.

Incidence of AEs and SAEs will be summarized by SOC and PT by treatment.

All AE data will be listed subject and treatment include the verbatim term entered by the Investigator.

